## **A 2 Financial disclosure**

Investigators and sub-investigators will provide the sponsor with sufficient, accurate financial information as requested to allow the sponsor to submit complete and accurate financial certification or disclosure statements to the appropriate regulatory authorities. Investigators are responsible for providing information on financial interests during the course of the study and for 1 year after completion of the study.

## **A 3 Informed consent process**

The investigator or his/her representative will explain the nature of the study to the subject or his/her legally authorized representative and answer all questions regarding the study.

Subjects must be informed that their participation is voluntary. Subjects or their legally authorized representative will be required to sign a statement of informed consent that meets the requirements of 21 CFR 50, local regulations, ICH guidelines, Health Insurance Portability and Accountability Act (HIPAA) requirements, where applicable, and the IRB/IEC or study centre.

The medical record must include a statement that written informed consent was obtained before the subject was enrolled in the study and the date the written consent was obtained. The authorized person obtaining the informed consent must also sign the ICF.

Subjects must be re-consented to the most current version of the ICF(s) during their participation in the study. A copy of the ICF(s) must be provided to the subject or the subject's legally authorized representative.

CCI

**During the COVID-19 pandemic.**

During the COVID-19 pandemic, re-consenting of subjects must follow local/regional guidelines with regard to informed consent. It is critical that where the written COVID-19 addendum to ICF cannot be obtained, and local/regional guidance allows, the subject's verbal consent via phone or teleconference is obtained before conducting any subject related changes implemented during the COVID-19 pandemic. Confirmation of subject's re-consent needs to be documented in the source documents. Refer to [Appendix H](#).

**A 4 Data protection**

Each subject will be assigned a unique identifier by the sponsor. Any subject records or data sets transferred to the sponsor will contain only the identifier; subject names or any information which would make the subject identifiable will not be transferred.

The subject must be informed that his/her personal study-related data will be used by the sponsor in accordance with local data protection law. The level of disclosure must also be explained to the subject.

The subject must be informed that his/her medical records may be examined by Clinical Quality Assurance auditors or other authorized personnel appointed by the sponsor, by appropriate IRB/IEC members, and by inspectors from regulatory authorities.

**A 5 Committees structure**

The safety of all AstraZeneca clinical studies is closely monitored on an on-going basis by AstraZeneca representatives in consultation with Subject Safety. Issues identified will be

Tezepelumab - D5180C00018

addressed; for instance, this could involve amendments to the Clinical Study Protocol and letters to Investigators.

## **A 6      Dissemination of clinical study data**

A description of this clinical trial will be available on *http://astrazenecagrouptrials.pharmacm.com* and *http://www.clinicaltrials.gov* as will the summary of the *main* study results when they are available. The clinical trial and/or summary of main study results may also be available on other websites according to the regulations of the countries in which the main study is conducted.

## **A 7      Data quality assurance**

All subject data relating to the study will be recorded on printed or electronic CRF unless transmitted to the sponsor or designee electronically (e.g., laboratory data). The investigator is responsible for verifying that data entries are accurate and correct electronically signing the CRF.

The investigator must maintain accurate documentation (source data) that supports the information entered in the CRF.

The investigator must permit study-related monitoring, audits, IRB/IEC review, and regulatory agency inspections and provide direct access to source data documents.

The sponsor or designee is responsible for the data management of this study including quality checking of the data.

Study monitors will perform ongoing source data verification to confirm that data entered into the CRF by authorized site personnel are accurate, complete, and verifiable from source documents; that the safety and rights of subjects are being protected; and that the study is being conducted in accordance with the currently approved protocol and any other study agreements, ICH GCP, and all applicable regulatory requirements.

Records and documents, including signed ICFs, pertaining to the conduct of this study must be retained by the investigator for 15 years after study completion unless local regulations or institutional policies require a longer retention period. No records may be destroyed during the retention period without the written approval of the sponsor. No records may be transferred to another location or party without written notification to the sponsor.

## **A 8      Source documents**

Source documents provide evidence for the existence of the subject and substantiate the integrity of the data collected. Source documents are filed at the investigator's site.

Tezepelumab - D5180C00018

Data reported on the CRF that are transcribed from source documents must be consistent with the source documents or the discrepancies must be explained. The investigator may need to request previous medical records or transfer records, depending on the study. Also, current medical records must be available.

Definitions of what constitutes source data can be found in the Source Data Agreement.

## **A 9      Publication policy**

The results of this study may be published or presented at scientific meetings. If this is foreseen, the investigator agrees to submit all manuscripts or abstracts to the sponsor before submission. This allows the sponsor to protect proprietary information and to provide comments.

The sponsor will comply with the requirements for publication of study results. In accordance with standard editorial and ethical practice, the sponsor will generally support publication of multicentre studies only in their entirety and not as individual site data. In this case, a coordinating investigator will be designated by mutual agreement.

Authorship will be determined by mutual agreement and in line with International Committee of Medical Journal Editors authorship requirements.

## **Appendix B Adverse event definitions and additional safety information**

### **B 1 Definition of adverse events**

An adverse event is the development of any untoward medical occurrence in a subject or clinical study subject administered a medicinal product and which does not necessarily have a causal relationship with this treatment. An AE can therefore be any unfavorable and unintended sign (e.g. an abnormal laboratory finding), symptom (for example nausea, chest pain), or disease temporally associated with the use of a medicinal product, whether or not considered related to the medicinal product.

The term AE is used to include both serious and non-serious AEs and can include a deterioration of a pre-existing medical occurrence. An AE may occur at any time, including run-in or washout periods, even if no Study treatment has been administered.

### **B 2 Definitions of serious adverse event**

A serious adverse event is an AE occurring during any study phase (i.e., run-in, treatment, washout, follow-up), that fulfils one or more of the following criteria:

- Results in death
- Is immediately life-threatening
- Requires in-subject hospitalisation or prolongation of existing hospitalisation
- Results in persistent or significant disability or incapacity.
- Is a congenital anomaly or birth defect
- Is an important medical event that may jeopardise the subject or may require medical treatment to prevent one of the outcomes listed above.

### **B 3 Life threatening**

‘Life-threatening’ means that the subject was at immediate risk of death from the AE as it occurred, or it is suspected that use or continued use of the product would result in the subject’s death. ‘Life-threatening’ does not mean that had an AE occurred in a more severe form it might have caused death (e.g., hepatitis that resolved without hepatic failure).

### **B 4 Hospitalisation**

Tezepelumab - D5180C00018

Outpatient treatment in an emergency room is not in itself a serious AE, although the reasons for it may be (e.g., bronchospasm, laryngeal oedema). Hospital admissions and/or surgical operations planned before or during a study are not considered AEs if the illness or disease existed before the subject was enrolled in the study, provided that it did not deteriorate in an unexpected way during the study.

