### 3 Objectives and Endpoints

**Table 3 Objectives and Endpoints**

Primary objective:	Outcome Measure:
To evaluate the long-term safety and tolerability of tezepelumab in severe asthma subjects	Exposure adjusted incidence rates of AEs/SAEs over 104 weeks
Secondary objective:	Outcome Measure:
To assess the long-term effect of 210 mg tezepelumab SC Q4W on asthma exacerbations in adult and adolescent subjects with severe uncontrolled asthma compared with placebo	Annualized asthma exacerbation rate (AAER) over 104 weeks (Baseline is week 0 in predecessor study)

CCI

Tezepelumab - D5180C00018

CCI

CCI

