## 4 Study Design

### 4.1 Overall design

For an overview of the study design see [Figure 1](#), in Section [1.3](#). For details on treatments given during the study, see Section [6.1](#) Treatments Administered.

For details on what is included in the safety and efficacy endpoints, see Section [3](#) Objectives and Endpoints.

This is a multicentre, randomized, double-blind, placebo-controlled, parallel group, long-term extension study to evaluate the safety and tolerability of 210 mg Q4W SC of tezepelumab in adults and adolescents with severe uncontrolled asthma. Subjects who have continued to receive investigational product and have attended the EOT visit in one of the predecessor studies may be eligible to enroll into this study if they fulfil the inclusion/exclusion criteria.

Tezepelumab - D5180C00018

This study will be run at approximately 350 sites worldwide and will randomize approximately 975 subjects worldwide. All subjects will be re-randomized in this study to maintain the blinding. Subjects previously randomized to the 210 mg tezepelumab Q4W SC arm in either of the predecessor studies, will be assigned and remain on 210 mg tezepelumab Q4W SC dosing in the LTE study. Subjects randomized to placebo arm in the predecessor studies will be re-randomized in a 1:1 ratio to either 210 mg tezepelumab or placebo, both administered Q4W SC. Given the randomization scheme of subjects in the predecessor studies, this will give an overall subject distribution of 3:1 (tezepelumab:placebo).

Subjects who prematurely discontinue IP or do not attend the EOT visit in one of the predecessor studies will not be eligible to participate in the Long-Term Extension (LTE) study.

In order to provide sufficient time for subjects to consider participation in this study, and to ensure an uninterrupted dosing regimen, as subjects transition between the predecessor study and this study, subjects will be provided with the ICF at/after the visit at which they receive their last dose of IP in the predecessor study and will be asked to sign the ICF at Visit 1 of this study prior to any study-specific procedures being performed.

Section 6.5 (Table 6 and Table 7) provides a list of medication restrictions and prohibitions to be followed throughout conduct of the clinical trial. See inclusion criteria Section 5.1.

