## 5 Study Population

Tezepelumab - D5180C00018

Prospective approval of protocol deviations to recruitment and enrolment criteria, also known as protocol waivers or exemptions, is not permitted.

Each subject should meet all of the inclusion criteria and none of the exclusion criteria for this study in order to be assigned/randomized to a study intervention. Under no circumstances can there be exceptions to this rule. Subjects who do not meet the entry requirements are screen failures and should therefore continue with the follow-up period as described in the protocol for the predecessor study, refer to Section 5.4.

In this protocol, “enrolled” subjects are defined as those who sign informed consent. “Randomized” subjects are defined as those who undergo randomization and receive a randomization number.

For procedures for withdrawal of incorrectly enrolled/randomized subjects see Section 7.3.

Subjects who are not able to attend an on-site EOT visit in the predecessor study/Visit 1 in the DESTINATION study due to the COVID-19 pandemic, are still allowed to roll-over to the DESTINATION study by the end of the safety follow-up of the predecessor study after confirmation of subject eligibility. Refer to Appendix H for further guidance.

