### 8.3.7 Adverse events based on examinations and tests

The results from the Clinical Study Protocol mandated laboratory tests and vital signs will be summarized in the CSR. Deterioration as compared to predecessor study baseline in protocol-mandated laboratory values and vital signs should therefore only be reported as AEs if they fulfil

Tezepelumab - D5180C00018

any of the SAE criteria or are the reason for premature discontinuation of treatment with the investigational product.

If deterioration in a laboratory value/vital sign is associated with clinical signs and symptoms, the sign or symptom will be reported as an AE and the associated laboratory result/vital sign will be considered as additional information. Wherever possible the reporting Investigator uses the clinical, rather than the laboratory term (e.g. anaemia versus low haemoglobin value). In the absence of clinical signs or symptoms, clinically relevant deteriorations in non-mandated parameters should be reported as AE(s).

Any new or aggravated clinically relevant abnormal medical finding at a physical examination as compared with the baseline assessment will be reported as an AE unless unequivocally related to the disease under study, see sections [8.3.9](#) and [8.3.10](#).

When collecting AEs, the recording of diagnoses is preferred, when possible, to recording a list of signs and symptoms. Asthma symptoms or signs, such as wheeze, cough, chest tightness, dyspnea, breathlessness and phlegm, will be recorded as AEs only when:

- The sign or symptom is serious according to definitions, see [Appendix B](#)
- The subject prematurely discontinues IP due to the sign or symptom
- The sign or symptom is new to the subject or not consistent with the subject's preexisting asthma history (defined as within 1 year of Visit 1 in predecessor study), as judged by the Investigator.

Asthma exacerbation should be recorded as an AE or SAE only if it fulfills any of the above criteria.

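### Appendix B 4 dates pre-existing illness from LTE consent (about Week 52/48), so a planned Year 2 admission for an illness that arose on treatment in Year 1 may not be recorded as serious

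*Protocol*

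**What the plan says.** Protocol Appendix B 4 sets an exemption with two conditions. Under the first, planned hospital admissions and operations "are not considered AEs if the illness or disease existed before the subject was enrolled in the study". The second condition is a proviso on worsening of the illness: the exemption applies "provided that it did not deteriorate in an unexpected way during the study".

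Section 5 fixes the meaning of the key word: enrolled "subjects are defined as those who sign informed consent". Section 4.1 fixes the date: subjects "will be asked to sign the ICF at Visit 1 of this study prior to any study-specific procedures being performed". Visit 1 normally coincides with the predecessor end-of-treatment visit, and inclusion criterion 3 also equates enrolment with Visit 1.

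The primary outcome in Table 3 is "Exposure adjusted incidence rates of AEs/SAEs over 104 weeks". Section 8.3.7, on which test results and asthma signs become AEs, uses a different reference from B 4. It speaks of "Deterioration as compared to predecessor study baseline" for laboratory values and vital signs, and counts pre-existing asthma history from Visit 1 of the predecessor study.

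**The concern.** The exemption is worded for a stand-alone trial, in which enrolment comes before the first dose. Here enrolment in the LTE study comes after 48 or 52 weeks of blinded tezepelumab or placebo. Applied with the protocol's own definitions, B 4 treats an illness that began on study treatment in Year 1 as if it had been present at baseline. A planned admission or operation for it in Year 2 then falls under the exemption.

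SAEs are part of the primary outcome, and inpatient hospitalisation is one of the criteria that make an AE serious (Appendix B 2). If the planned admission is set aside under B 4, a treatment-emergent illness that led to inpatient care inside the 104-week window may stay classified as non-serious.

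**Working it through.** The plan states no figure on this point, so the check is of the text, with one small piece of arithmetic.

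1. **When enrolment falls.** Section 5 (consent) and section 4.1 (consent at Visit 1) together place it at Week 52 for D5180C00007 and Week 48 for D5180C00009, or later for roll-overs delayed under Appendix H. The part of the 104-week window before that date is 52/104 = 50% and 48/104 = 46%. Any illness with onset in that part is pre-existing under B 4.

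2. **Reference points side by side.**

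| Rule | Reference point |
|---|---|
| Safety analyses, overall (9.4.2) | Week 0 to Week 104 |
| Safety baseline (9.4.1) | First predecessor dose |
| Laboratory and vital-sign deterioration (8.3.7) | Predecessor baseline |
| Pre-existing asthma history (8.3.7) | Predecessor Visit 1 |
| Planned admissions (B 4) | Enrolment in the study, that is, LTE consent |

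   Only B 4 starts its clock at LTE entry.

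3. **Is the illness itself lost?** No. Table 1, footnote a, links AEs to the predecessor record. Section 8.3.2 collects ongoing predecessor AEs again in the LTE. SAP 3.1.1 combines the two records where possible, keeping the worst case. A Year 1 illness is therefore already an AE in the 104-week analysis.

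4. **Is its seriousness preserved?** Not reliably. B 2 makes an AE serious if it requires hospitalisation, and section 8.3.4 collects the date on which an AE became serious, so later upgrading is foreseen. B 4, however, tells the site that this admission is not an AE. If the site therefore records nothing as serious, the worst-case merge has no serious record to carry forward.

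5. **Which admissions are affected?** Only planned ones, for an illness with onset before LTE consent, without unexpected deterioration. Unplanned admissions are outside the exemption, and so are illnesses that first arise in Year 2. Exclusion criterion 6 removes much surgery already planned at entry, and criterion 4 removes most malignancies that developed in a predecessor study. What remains is procedures planned after entry, cases approved by the sponsor, and procedures below the threshold of criterion 6.

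6. **Where would a missing SAE appear?** SAP 3.2.2 assigns AEs to periods by onset date and counts subjects, not events. Where the records are merged, the upgraded AE would belong to the predecessor period and to the overall 104-week rate. It would change the rate only if the subject had no other SAE in the period concerned.

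**The case against.** The best defence is that B 4 exempts the admission and says nothing about the illness. An AE carried over from Year 1 that then requires hospitalisation still meets B 2, and the form has a field for the date on which it became serious. Medical history is summarised at predecessor study entry (9.4), so a Year 1 illness sits in the record as an AE and not as history. A site might also read the loose wording about a study and the study as meaning the combined programme.

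Part of this stands. It shows that loss of the SAE is possible, not certain, and that some sites would upgrade correctly. It does not remove the problem: the protocol's own definition of enrolment points to LTE consent, and if sites read the rule differently, SAE classification will differ between sites.

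A reader might infer that B 4 removes Year 2 hospitalisations in general from the AE and SAE counts. The documents do not support that. The illness remains an AE, and the exemption covers only planned admissions without unexpected deterioration. Nor does it touch late-onset illness, which is a main interest of a long-term extension.

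**Conclusion.** The reference point in B 4 is out of line with the 104-week outcome and with section 8.3.7. The consequence is possible under-classification of SAEs in a narrow set of planned Year 2 admissions. There should be hardly any effect on AE rates. The documents give no rate of planned admissions, so the number of SAEs affected cannot be estimated.

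A reader might also infer a calculable bias in favour of tezepelumab. With the planned roll-over of 0.90 × 0.90 = 0.81, equal years and no LTE dropout (D5180C00007), LTE follow-up is 0.81/1.81 = 45% of Randomised Tezepelumab and 0.405/1.405 = 29% of Randomised Placebo. Turning these shares into a shift of the SAE rate ratio would need a fraction of exempted SAEs that no document supplies. It would also place the lost SAEs in LTE time, whereas the SAP assigns AEs by onset date. On that rule, a Year 1 illness in a subject who later switched from placebo could still belong to Randomised Placebo, so even the imbalance between groups is not established.

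The conclusion rests on reading enrolled as section 5 defines it, and on some sites following B 4 literally. The change is worth considering, with moderate confidence. No hypothesis is formally tested, so no test result depends on it.

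**What to change.** In Appendix B 4, make the illness condition refer to enrolment in the predecessor study (D5180C00007 or D5180C00009), and make the deterioration proviso cover the predecessor or LTE study. Tell the sites. Before primary database lock, query recorded LTE admissions and operations that were not reported as SAEs and whose underlying illness began after the first predecessor dose.

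The cost is a change of two phrases, a site memo and a small data query, with no added visits or tests. The reported SAE rate may rise slightly. The query reaches only admissions that were recorded somewhere in the study data.

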## **B 5 Important medical event or medical treatment**

Medical and scientific judgement should be exercised in deciding whether a case is serious in situations where important medical events may not be immediately life threatening or result in death, hospitalization, disability or incapacity but may jeopardize the subject or may require medical treatment to prevent one or more outcomes listed in the definition of serious. These should usually be considered as serious.

Simply stopping the suspect drug does not mean that it is an important medical event; medical judgement must be used. Examples of such events are:

- Angioedema not severe enough to require intubation but requiring iv hydrocortisone treatment
- Hepatotoxicity caused by paracetamol (acetaminophen) overdose requiring treatment with N-acetylcysteine
- Intensive treatment in an emergency room or at home for allergic bronchospasm
- Blood dyscrasias (e.g., neutropenia or anaemia requiring blood transfusion, etc.) or convulsions that do not result in hospitalisation
- Development of drug dependency or drug abuse

